# Introduction or Background

#### Problem and Purpose Statement-Objective of the Research

The aim of this project was to determine whether fentanyl and morphine have similar effects in reducing aspirin's effect upon platelets in emergency department patients with chest discomfort. Morphine has been shown to worsen outcomes in heart attack patients due to reduction of oral anti-platelet agent effectiveness and so many providers have switched to using fentanyl. However, it is largely unknown whether fentanyl has similar effects.

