## **Research Questions or Hypothesis**

It is unlikely that a sufficient sample of patients with acute coronary syndrome (ACS) can be obtained to prospectively compare fentanyl to morphine, as the administration of other anticoagulants would confound the results. Therefore, the study will focus on chest pain patients in the emergency department. The hypothesis is that both morphine and fentanyl will reduce the effectiveness of aspirin.

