# **Data Analysis Procedure**

In the PACIFY trial, at 2 hours, patients receiving fentanyl had a PRU value of 113 +/- 94 on the platelet aggregation study (light aggregometry using ADP) after receiving Brilinta (ticagrelor), versus 71 +/- 66 in those not receiving fentanyl. With an alpha of 0.05 and beta of 0.8, 57 patients would be required to demonstrate statistical significance if there is a similar magnitude of effect. In the PERSEUS trial at 2 hours, patients receiving fentanyl had a PRU value of 173 +/-90 after also receiving Brilinta (ticagrelor), versus 210 +/- 76 in those receiving morphine and Brilinta (ticagrelor). 74 patients would be required to show statistical significance in direct comparison of morphine vs fentanyl. The aim is to enroll 80 patients in each arm (no narcotic, morphine, and fentanyl).

Two-tailed T-testing will be used to look for differences in the 2 hour platelet reactivity response rates between those receiving morphine versus those not receiving narcotics and between those receiving fentanyl and those not receiving narcotics.

If the data is sent to the Spectrum Health SASS team for analysis MRN's will be converted to a study ID so that the actual MRN will not be sent out.

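### The aim is whether fentanyl and morphine act alike, but the only planned tests are each drug against no narcotic, and significance results, including a null direct test, cannot show similarity

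*Combined protocol and SAP*

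**What the plan says.** Three statements in the combined protocol and SAP bear on this point.

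- **Aim** (Problem and Purpose Statement): to "determine whether fentanyl and morphine have similar effects" on aspirin's platelet action.
- **Hypothesis** (Research Questions or Hypothesis): "The hypothesis is that both morphine and fentanyl will reduce the effectiveness of aspirin". This is a statement about each drug against no narcotic, not about one drug against the other.
- **Analysis** (Data Analysis Procedure): "Two-tailed T-testing will be used to look for differences in the 2 hour platelet reactivity response rates". The section names two contrasts: morphine against no narcotic, and the contrast "between those receiving fentanyl and those not receiving narcotics".

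The Data Analysis Procedure also gives a sample size for the head-to-head contrast: "74 patients would be required to show statistical significance in direct comparison of morphine vs fentanyl". That contrast does not reappear among the tests. The documents contain no similarity margin, no confidence-interval criterion and no statement of how a non-significant result would be interpreted.

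**The concern.** The aim is about how the two opioids compare with each other. The planned inference never compares them. A report written from this plan would have to judge similarity from the pattern of two p-values against a shared control, or from a direct test added later. Neither supports the conclusion. Two drugs can both differ from control and still differ materially from each other, and failing to find a difference is not evidence that it is small.

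The stakes are practical. The Problem and Purpose Statement says that many providers have already moved from morphine to fentanyl, so readers will look to this study for how the two compare.

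**Working it through.** **Inputs**, all from the Data Analysis Procedure. The ± values are read as SDs and the sample sizes as per arm.

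- Fentanyl vs none (PACIFY): 113 ± 94 vs 71 ± 66, difference 42 PRU, stated n 57.
- Morphine vs fentanyl (PERSEUS): 210 ± 76 vs 173 ± 90, difference 37 PRU, stated n 74.
- "With an alpha of 0.05 and beta of 0.8", read as two-sided 5% and power 80%. Planned enrolment is 80 per arm.

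**1. The plan's own figures.** n per arm = 2 × [SD × (1.960 + 0.842) / difference]².

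- PACIFY, SD = (94 + 66)/2 = 80: 2 × (80 × 2.802/42)² = 57.0, so 57. This reproduces.
- PERSEUS, SD = √((90² + 76²)/2) = 83.3: 2 × (83.3 × 2.802/37)² = 79.6, so 80, not 74. An SD of 80 gives 73.4, so 74. This is a side matter, because 80 per arm gives about 80% power for 37 PRU.

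Both figures are sizes for detecting a difference.

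**2. Precision at 80 per arm.** SE of a difference = 83.3 × √(2/80) = 13.17 PRU.

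**3. What the two planned tests can show.** Simulation of 20,000 trials, normal data, SD 83.3 in every arm, 80 per arm:

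| True effects vs none (morphine, fentanyl) | Both significant | One only | Neither |
|---|---|---|---|
| 42 and 42 (identical) | 81% | 15% | 4% |
| 79 and 42 (37 apart) | 89% | 11% | 0% |

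A hand check of the second row: 42/13.17 = 3.19, and Φ(3.19 − 1.975) ≈ 0.89. The 79 PRU effect, at 79/13.17 = 6.0 SEs, is almost always significant. In these two scenarios, both tests being significant is more common when the drugs differ by 37 PRU than when they are identical. The pattern therefore cannot support a claim of similarity.

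**4. What a direct t-test would show if added.** The 95% half-width is 1.975 × 13.17 = 26.0 PRU. The chance of a non-significant result is:

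| True difference (PRU) | 18.5 | 25 | 30 | 37 |
|---|---|---|---|---|
| Non-significant | 71% | 53% | 38% | 20% |

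**5. What a formal margin would require.** The documents give no margin, so the values of M here are assumptions. If the drugs are truly identical, the chance that the interval falls inside ±M is 2Φ(M/13.17 − z) − 1.

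| M (PRU) | 90% interval (z = 1.645) | 95% interval (z = 1.960) | n per arm for 80% power, 90% interval |
|---|---|---|---|
| 37 | 76% | 60% | 87 |
| 30 | 47% | 25% | 133 |
| 25 | 20% | 0% | 191 |
| 18.5 | 0% | 0% | 348 |

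**The case against.** The best defence is that the aim is loosely worded. The Problem and Purpose Statement goes on to say that it is unknown whether fentanyl shares morphine's effect, which can be read as asking whether fentanyl interferes with aspirin too. The hypothesis section says much the same, and difference tests against no narcotic suit that hypothesis. This stands, and it is why rewording the aim is an acceptable remedy. It does not remove the inconsistency, because the aim still names similarity and the Data Analysis Procedure still sizes a direct comparison.

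A reader might go further and infer that the plan will declare similarity from a p-value above 0.05, so that a noisier or smaller study reaches that claim more easily. The documents do not support this. No morphine-fentanyl test is planned, so there is no such p-value, and nothing says a null result would be read that way. For the tests that are listed, noise makes support for the hypothesis harder to obtain, not easier. The literature review does describe a 38-patient trial as showing no difference at 2 hours, but that concerns another study and is only indirect support.

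It is also tempting to prescribe 37 PRU (37/83.3 = 0.44 SD) as the similarity margin. That figure comes from ticagrelor patients, equals the difference the study was sized to detect, and has no clinical justification in the documents as a margin.

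**Conclusion.** The concern holds in this form: the aim and the planned analysis do not match, and neither the two listed tests nor a non-significant direct test could establish similarity. At 80 per arm, drugs 37 PRU apart would both be significant against no narcotic in about 89% of trials if their true effects were 79 and 42. A direct comparison would carry an uncertainty of about ±26 PRU and would miss a true 18.5 PRU difference about 71% of the time.

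These sizes assume that the ± values are SDs, that an SD of 83.3 applies in every arm, that means are roughly normal, and that no samples are lost. They are on the PRU scale of ticagrelor trials, whereas this study measures arachidonic-acid aggregation after aspirin. They show the scale of the problem and do not predict this study's results.

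**What to change.** In the Data Analysis Procedure, add:

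> The morphine minus fentanyl difference in 2-hour platelet aggregation will be estimated with its 95% confidence interval. Similarity will not be concluded from a non-significant difference, nor from both narcotics differing significantly from no narcotic. An interval that includes differences as large as the one the study was sized to detect will be reported as inconclusive on similarity.

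The sponsor should state that difference on the arachidonic-acid assay's scale before the data are analysed.

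Alternatively, reword the aim to match the hypothesis, namely whether each narcotic reduces aspirin's effect, and make no statement about similarity.

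If a formal similarity claim is wanted, the sponsor should justify a margin on the assay's own scale and state the power for it.

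The first two options cost a few sentences and at most one interval, with no extra patients or assays. The downside is that similarity becomes harder to claim: on the illustrative figures, even identical drugs would give an inconclusive interval in about 40% of trials (100% − 60%, the 95% interval at 37 PRU). A formal claim with 80% power could need more than 80 per arm. Because the treating clinician chooses the analgesic, an unadjusted interval describes the groups compared and does not by itself attribute similarity to the drugs.

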### Theoretical Framework-Present Knowledge, Literature Review

Patients experiencing heart attacks or unstable angina (commonly known as acute coronary syndrome (ACS)) commonly experience discomfort and pain. Nitroglycerin is typically the first medicine given for discomfort because it has dilatory effects upon vasculature to reduce the blood pressure and relax blood vessels to decrease myocardial demand. However, in some patients it is contraindicated and in many patients it is only partially efficacious in reducing discomfort. Narcotics are commonly given. Classically morphine was given in ACS as it is also thought to have venodilatory properties and could perhaps also relax the patient to decrease the sympathetic demands of the frightfight-flight responses experienced by patients having heart attacks. Narcotics have several common side effects, and one of these is decreased gastrointestinal (GI) transit time, commonly manifested as constipation. However, this decreased GI transit time also can slow the absorption of oral medications. Oral anti-platelet therapy (starting with aspirin and commonly including dual anti-platelet therapy with clopidogrel as well) is also part of the treatment of patients with ACS as reducing clot propagation in the coronary arteries can decrease the size of an infarct. Interference with oral anti-platelet therapy has been observed with morphine (2) contributing to worse outcomes in patients receiving morphine (1). Delayed onset of action or decreased absorption has also been demonstrated with stronger anti-platelet drugs such as clopidogrel (3) and prasugrel (4) in association with morphine. Many physicians have therefore switched to using fentanyl, and fentanyl has been found to be equally efficacious in pain control in potential ACS (7). The PACIFY trial (5) evaluated the effects of fentanyl upon the stronger anti-platelet agent ticagrelor and found statistical significance at 2 hours with a lower peak concentration, and delayed onset of the peak concentration of ticagrelor when fentanyl was given. The PACIFY trial did not compare the effects of morphine to fentanyl. The PERSEUS trial was a small study of 38 patients (6) which showed no difference between fentanyl and morphine at 2 hours with regards to ticagrelor absorption but that there was a difference at 4 hours. There has not to our knowledge been any study of fentanyl's effect on aspirin absorption.

## **Research Questions or Hypothesis**

It is unlikely that a sufficient sample of patients with acute coronary syndrome (ACS) can be obtained to prospectively compare fentanyl to morphine, as the administration of other anticoagulants would confound the results. Therefore, the study will focus on chest pain patients in the emergency department. The hypothesis is that both morphine and fentanyl will reduce the effectiveness of aspirin.

## Methodology

Given the challenges in obtaining a sufficient sample of patients with acute coronary syndrome (ACS) to prospectively compare fentanyl to morphine, the study will focus on chest pain patients in the emergency department. These patients typically have blood drawn initially and again two hours later to check for elevation and changes in troponin levels, a cardiac muscle protein detectable when cardiac muscle is being injured. These blood draws will be supplemented by evaluating platelet aggregation at the 0 and 2-hour marks.

There are many measures and techniques in evaluation of platelet function. Light Transmission Aggregometry (LTA) looks at changes in light transmittance through serum as platelets aggregate, leading to increased light transmission as more platelets aggregate. Aspirin interferes with arachidonic acid mediated aggregation because of its effects upon COX-1 conversion of arachidonic acid to thromboxane A2. Arachidonic acid is therefore the best trigger to use to evaluate aspirin's effect upon platelets, as opposed to epinephrine, ADP, or several others used to evaluate the stronger anti-platelet oral and IV agents that act in different places in the platelet activation cascade (8).

#### **Research Design**

Patients who have 0 and 2 hour troponins ordered will have their chart reviewed by the research coordinator for candidacy in the study (see below for inclusion/exclusion). If the patient meets study entry criteria then platelet aggregation studies using arachidonic acid will be added on to the 0 and 2 hour lab draw.

The study will compare the 0 and 2-hour platelet aggregation scores of patients receiving aspirin who are undergoing two sets of troponin tests. The first group will consist of patients not receiving any narcotics, the second group will include those receiving morphine, and the third group will include those receiving fentanyl. The treating clinician will determine the appropriate pain treatment plan for each patient.

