### Sample/Participants

The research coordinator will perform chart review on Emergency Department patients presenting with chest discomfort. If there are 2 sets of troponins ordered and no exclusion criteria then the research coordinator will approach the patient for consent.

Inclusion criteria: Adult Emergency Department patients undergoing 0 and 2 hour troponin testing who have been administered aspirin within 30 minutes of the initial blood draw. Initially all patients undergoing this testing will be candidates for the study. We will attempt to enroll 80 patients in the each of the 3 arms. Determination of which (if either) narcotic is administered will be up to the clinician. As we reach the enrollment goals our research coordinator will discuss with the clinicians the expected pain plan to tailor enrollment of patients in the treatment arms that are still needed

Exclusion criteria: Patients not expected to get a 2 hour troponin; patients already on aspirin, clopidogrel, or stronger anti-coagulants; patients who arrived via EMS given it can be difficult to find the run reports to determine whether patient received fentanyl in the pre-hospital period; pregnant patients; patients on chronic narcotics; patients already once enrolled in this study, inability to provide consent in English

With regards to at risk populations, Economically Disadvantaged, Nursing home residents, prisoners, homeless patients are all commonly encountered in the ED. However, the request of 1 or 2 blue top tubes (totaling about a teaspoon of blood) is not an onerous ask. Since narcotic use (or non-use) will be wholly up to the provider and not impacted by this study we see no problems with including them.

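### The clinician chooses the narcotic, but the planned t-tests make no adjustment for the reason a narcotic was given

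*Combined protocol and SAP*

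**What the plan says.** **Allocation.** Research Design states: "The treating clinician will determine the appropriate pain treatment plan for each patient". Sample/Participants repeats it: "Determination of which (if either) narcotic is administered will be up to the clinician".

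**Hypothesis.** Research Questions or Hypothesis words the aim causally: "The hypothesis is that both morphine and fentanyl will reduce the effectiveness of aspirin".

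**Analysis.** Data Analysis Procedure is the only analysis text: "Two-tailed T-testing will be used to look for differences in the 2 hour platelet reactivity response rates". It names two contrasts, each narcotic against no narcotic. It mentions no covariate, stratification, matching, propensity method or sensitivity analysis.

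**Data.** Instrumentation-Data collection lists age, sex, race, ethnicity, haemoglobin, platelet count, creatinine, and the time and dose of aspirin and of narcotics. Creatinine is there to describe the population, and no variable is given a role in adjustment. Pain score and nitroglycerin use are not listed. Research Design says that 0-hour and 2-hour scores will be compared, but the planned test uses only the 2-hour value.

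**Restrictions.** Sample/Participants excludes patients already on aspirin, clopidogrel or stronger anticoagulants, EMS arrivals and "patients on chronic narcotics". It admits only patients "who have been administered aspirin within 30 minutes of the initial blood draw".

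**The concern.** A two-group t-test attributes the whole difference between arms to the narcotic. That is sound when chance decides who gets the drug. Here a clinician decides, presumably in response to the patient's condition, so patients given a narcotic may differ from the others before any drug acts. If whatever prompts the narcotic is also related to platelet aggregation two hours after aspirin, the t-test mixes the two effects. Bias in one direction produces false positives. Bias in the other hides a real effect, so a null result would be as hard to read as a positive one. A larger sample does not help, because it shrinks random error and leaves bias where it is.

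The only confounding the protocol names is that from other anticoagulants in ACS patients, in Research Questions or Hypothesis. The reason for giving a narcotic is not addressed anywhere.

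**Working it through.** **1. The plan's own figure.** Data Analysis Procedure gives 57 patients for fentanyl against no fentanyl, from means of 113 (SD 94) and 71 (SD 66). I read the stated beta of 0.8 as power of 0.80, and 57 as a number per arm.
- n = 2 × [SD × (1.960 + 0.842) / difference]²
- Difference = 113 − 71 = 42. With SD 80, the simple mean of 94 and 66, n = 57, which reproduces.
- With the root-mean-square SD, √((94² + 66²)/2) = 81.2, n = 59.

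This calculation covers random error only and says nothing about confounding.

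**2. Standard error at the planned size.** With 80 per arm and equal SDs, SE of a difference = √(2/80) = 0.158 SD. In SD units this does not depend on the assay scale, so it applies to both planned contrasts.

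**3. Effect of an assumed bias b, with no true drug effect.** Rejection rate = 1 − Φ(1.96 − b/0.158) + Φ(−1.96 − b/0.158).

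| Assumed bias (SD) | Two-sided false-positive rate |
|---|---|
| 0 | 5.0% |
| 0.10 | 9.7% |
| 0.25 | 35.3% |

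The bias sizes are assumptions; the documents supply none.

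**4. What would produce such a bias.** For a single confounder, bias ≈ imbalance between arms × slope on the outcome.
- Imbalance 0.5 SD, slope 0.2 SD per SD: 0.5 × 0.2 = 0.10 SD.
- Imbalance 1 SD, slope 0.25 SD per SD: 1 × 0.25 = 0.25 SD.

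A simulation with three arms of 80, no drug effect and 2,000 runs gave false-positive rates of 10.1% unadjusted and 5.1% adjusted in the first case, and 33.3% and 4.5% in the second. The second unadjusted rate is below 35.3% because the simulation fixes the residual SD at 1. The total SD is then √(1 + 0.25²) = 1.03, and the bias is 0.25/1.03 = 0.243 SD. The adjusted rates hold only when the confounder is measured and correctly modelled.

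**5. Precision cost of adjustment.** Suppose both narcotic arms differ from the no-narcotic arm by d SD in pain score, and pain score is the only imbalanced covariate. Then SE = √(2/80 + d²/237), where 237 = 240 − 3. Power is for fentanyl against none at 42/81.2 = 0.517 SD.

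| d (SD) | SE (SD) | Ratio to unadjusted | Power |
|---|---|---|---|
| 0 | 0.158 | 1.00 | 90.5% |
| 0.5 | 0.161 | 1.02 | 89.3% |
| 1 | 0.171 | 1.08 | 85.7% |

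The plan gives no planning effect for morphine against none, so no power is stated for that contrast. The 0.517 SD comes from ticagrelor data, and its transfer to aspirin is the plan's assumption.

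**6. Degrees of freedom.** With complete data and ten covariates entered as single terms, 240 − 3 − 10 = 227 remain. Adding the 0-hour value leaves 226.

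**The case against.** The strongest reply is that no confounding has been shown. No passage links pain severity, or any other reason for giving a narcotic, to arachidonic-acid aggregation after aspirin. The error rates above would apply to any non-randomised comparison with 80 per arm. This stands, and it limits the point to a missing safeguard.

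A reader might infer more from the literature review, which says of nitroglycerin: "in many patients it is only partially efficacious in reducing discomfort. Narcotics are commonly given". That would suggest that narcotic patients here are those in whom nitroglycerin failed. But the passage describes ACS, and the protocol says it studies emergency department chest-pain patients because an adequate ACS sample is unlikely. It makes a patient-driven choice plausible; it does not establish one in this population.

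A reader might also cite "Many physicians have therefore switched to using fentanyl". That concerns the choice between fentanyl and morphine, whereas the planned tests compare each drug with no narcotic. It also describes physician habit and not a patient characteristic, so it does not support the point.

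The eligibility rules do control some confounding, by excluding prior antiplatelet use and chronic narcotics and by limiting aspirin timing. Credit is due, but none of them concerns why a narcotic is given during the visit.

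Finally, adjustment can look more thorough than it is. Age, sex and laboratory values say little about indication, so a model limited to the listed variables would miss the main issue. This objection is sound, and it is why the fix needs indication variables.

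**Conclusion.** The omission is certain on the text: allocation is by clinician choice, the hypothesis is causal, and the stated method cannot separate the drug from the reason it was given. This is more than missing detail, because a method is specified and a better one is available at little cost.

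Whether material bias exists is not known. A reader might conclude that the study's results will be biased, or will be false positives. The documents do not support that, since neither size nor direction can be derived from them. The figures of about 10% at 0.10 SD and about 35% at 0.25 SD rest on assumed biases, equal SDs and 80 per arm. They show how little bias would matter at this sample size, not how much there is.

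The point should be fixed before analysis, as a cheap improvement. It is not a reason to regard the design as unusable.

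**What to change.** In Data Analysis Procedure:

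- **Primary analysis.** Prespecify one linear model of 2-hour aggregation on arm, with no narcotic as reference. Adjust for age, sex, platelet count, haemoglobin, creatinine, aspirin dose, and aspirin time relative to the first draw. Add three pre-narcotic indication variables from the chart: first emergency department pain score, nitroglycerin given before any narcotic, and initial troponin, which every eligible patient has. Define each the same way in all arms, including for patients who never receive a narcotic.
- **Sensitivity analysis.** Keep the planned t-tests as the unadjusted analysis.
- **Second model.** Add the 0-hour value, which Research Design says will be compared. Keep this model secondary: aspirin may be given within 30 minutes of that draw, so the value may already reflect aspirin.
- **Actual time to the 2-hour draw.** Use it only in a sensitivity analysis, because it can be set after the narcotic is given.
- **Wording.** State conclusions as associations.

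The cost is a few chart fields, some missing pain scores and a modest loss of precision. If pain score alone differs between the narcotic and no-narcotic arms by 0.5 or 1 SD, the SE rises by about 2% or 8%, and fentanyl-against-none power falls from about 90% to 89% or 86%. Imbalance in the other covariates could add to that loss, and covariates that predict the outcome could offset it. Treatment, blood draws and sample size need not change. Residual confounding will remain and should be stated as a limitation.
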